- [name], Assistant Professor, General Internal Medicine (Co-I)

Preliminary Data

Hospital Discharge Study

This was a randomized study of hospitalized insulin-requiring patients with T2D and A1c >8.5%. All subjects received study-supplied insulin glargine 300 U/mL (Gla-300). The intervention consisted of an electronic discharge order set (DOS) and periodic phone calls from the study nurse. The primary outcome was change in A1c from baseline to 24 weeks following discharge.

Results: The study was stopped early due to feasibility concerns during the pandemic. A total of 158 subjects were enrolled (DOS=82, ESC=76, Table 1). The DOS group had a greater frequency of new prescriptions for bolus insulin and testing supplies but no difference in order clarity. A1c was available in 27 subjects in each arm at 12 weeks, and 20 and 21 subjects in the DOS and ESC arms, respectively at 24 weeks. The adjusted difference in change in A1c (DOS-ESC) was $-0.5 \pm 0.4\%$ at 12 weeks (adjusted p-value 0.20) and $-0.7 \pm 0.4\%$ at 24 weeks (adjusted p-value 0.09). Achievement of individualized A1c target was greater in the DOS group at 12 weeks but not 24 weeks, after the intensity of follow-up had decreased, underscoring the need for ongoing high frequency care.²⁶ In post-hoc analysis, functional health literacy,

Table 1. Baseline Characteristics, Hospital Discharge Study

| | Overall N=158 | Enhanced Standard Care (N=76) | Discharge Order Set (N=82) |
|---|------------------|----------------------------------|-------------------------------|
| Age (years) | 51.7 (10.2) | 51.4 (10.5) | 52 (10.1) |
| Male | 68 (43.0) | 33 (43.3) | 35 (42.7) |
| White^{1,2} | 74 (46.8) | 34 (44.7) | 40 (48.8) |
| Hispanic | 3 (1.9) | 1 (1.3) | 2 (2.4) |
| Diabetes duration (years) | 11 (7, 20) | 14 (7, 20) | 10 (6, 15) |
| Body mass index (kg/m²) | 38.2 (9.5) | 38.1 (8.7) | 38.4 (10.1) |
| Estimated Glomerular Filtration Rate | | | |
| >60 | 109 (69.0) | 51 (67.1) | 58 (70.7) |
| 30-60 | 39 (24.7) | 21 (27.6) | 18 (22.0) |
| <30 | 107 (6.3) | 4 (5.3) | 6 (7.43) |
| Education | | | |
| Less than high school | 15 (9.5) | 10 (13.2) | 5 (6.1) |
| High school or equivalent | 118 (74.7) | 55 (72.4) | 63 (76.8) |
| Bachelor's degree | 25 (15.8) | 11 (14.5) | 14 (17.1) |
| Insurance | | | |
| None | 11 (7.0) | 7 (9.2) | 4 (4.9) |
| Private | 52 (32.9) | 22 (29.0) | 30 (36.7) |
| Medicare | 35 (22.1) | 18 (23.7) | 17 (20.7) |
| Medicaid | 60 (38.0) | 29 (38.2) | 31 (37.8) |

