| Diabetes history | x | | | | | | | |
| Hospitalization history | x | | | | | | | |
| MSPSS scale | x | | | | | | | |
| eHEALS score | x | | | | | | | |
| SNS3 | x | | | | | | | |
| DTSQ (original plus change at screen and week 12) | | | | | x | | | |
| DDS | x | | | | x | | | |
| BenCGM, BurCGM | | | | | x | | | |
| Additional patient questions | | x | x | x | x | | | x |
| Patient barriers | | | | | | | | x |
| Ascertain health care utilization | x | x | x | x | x | x | x | x |
| Record CGM data | | x | x | x | x | | | x |
| Adverse events | | x | x | x | x | x | x | x |
| Insulin/DM medication use | x | x | x | x | x | x | x | x |
| A1c | x | | | | x | | | x |
| Usual Provider Survey | | | | | x | | | |

CMN=certificate of medical necessity, MSPSS=Multidimensional Scale of Perceived Social Support, eHEALS=eHealth Literacy Scale Diabetes, DTSQ=Diabetes Treatment Satisfaction Questionnaire, BenCGM=Benefit of CGM score, BurCGM=Burdens of CGM score,

DDS=Diabetes Distress Scale, SNS3=Subjective Numeracy Scale-3. In-Person clinic visits will be conducted at either Outpatient Care East or McCampbell Hall. Telephone visits may be converted to in-person visits as needed.

Initial Assessment: Trained interviewers will perform initial data collection.

- Contact information, including email address, best times to reach the patient, contact information for 2 additional individuals, and primary care provider (PCP).
- Demographics, medical, social history
- Multidimensional Scale of Perceived Social Support (MSPSS): Social support is an environmental factor that is associated with readmissions⁴⁹, determines behavior in SCT and influences self-efficacy⁵⁰ and will be measured using the MPSS.⁵¹
- Electronic health literacy: Baseline perceived eHealth literacy will be measured by the eHealth Literacy Scale (eHEALS), in which a score of 28 was used as the cut-off for high or low ehealth literacy.⁵² The scale is comprised of 8 items on a 5-point Likert scale from 1 (strongly disagree) to 5 (strongly agree).
- Subjective Numeracy Scale-3 (SNS-3): The SNS-3 is a validated 3-item version of the longer SNS that was found to be reliable and valid to be used as a measure of subjective numeracy.⁵³

- Comorbidity is key determinant of readmission; it is measured with the Charlson comorbidity index.⁵⁴

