 - **Inclusion/exclusion criteria:** The patient's usual care provider (primary care or endocrinologist) will be identified from the electronic medical record and via patient self-report. Providers will be invited to anonymously respond to the survey via an electronic communication (Inbox message, email, or letter with a URL link—in case of external provider).
- **Week 1, 2, 4, 8, and 12:**
 - **Patients NOT meeting targets:** At 1-2, 4, 8, and 12 weeks, the study team will:
 - Provide advice to the patient on basal insulin titration.
 - Counsel patient on therapeutic lifestyle changes
 - Provide a letter with a summary of the CGM interpretation and counseling provided to the patient as well as any additional advice to the usual diabetes care provider using a standardized template. The letter will include a copy of the Ambulatory Glucose Profile and the Glucose Overlay from the previous 14 days.
 - **Patients meeting targets:** a summary letter with Ambulatory Glucose Profile will be sent to usual care providers at weeks 1-2, 4, 8, and 12.
- **Week 8:** In preparation for transitioning patient to the extension phase of the study, the usual care provider will be sent instructions for prescribing the CGM device, including a pre-filled certificate of medical necessity, if applicable.

Follow-up Encounters: Patients will be contacted 1-2 weeks after discharge to confirm CGM use and address any concerns. If needed, this visit can be converted to in-person if additional supplies and/or training is needed. Thereafter, in-person visits are only required for the completion of A1c and patient reported outcomes surveys and other visits can be completed via telephone call. Dexcom supplies will be shipped directly to patients monthly or can be picked up by the patient. CGM data will be reviewed on Clarity and sent to the usual diabetes care provider after every visit as noted above. Diabetes medications and healthcare utilization will also be reviewed at each visit. At the 12 week visit, patients will complete patient-reported outcomes surveys and A1c.

Study Completion

Participants will receive an order to complete the A1c at 12 weeks via point-of care assay. They will be asked to complete additional surveys (Table 5). The study team will complete the 12 week visit and send a final communication to the healthcare provider with a summary of the visit, notice of study completion with study extension phase, the patient's Clarity sharecode, and CGM report.

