- Usual Care Provider usability: SUS-2 (ease of use, cumbersome to use), CGM report helpful in assessing glucose control, ambulatory glucose profile helpful for making adjustment in therapy, report recommendations helpful for making adjustments to therapy, whether Clarity website was accessed.
- % of usual care providers reporting review of data

Aim 3:

Primary:

- Change in DTSQ scores from baseline to 12 weeks

Secondary:

- Change in DDS from baseline to 12 weeks
- Patient reported outcomes (DTSQ, DDS, BenCGM, BurCGM).

Endpoints for Exploratory Aim 1:

- healthcare utilization (clinic visits, education visit, hospital readmission, emergency visit)

Endpoints for Exploratory Aim 2 (Extension Phase): *By 18 months (the end of the last 90 day visit), we anticipate that a subset of patients (75%) will have at least 12 additional weeks of data following the primary endpoint at 12 weeks. We will assess the following metrics among users and compare to nonusers:*

- Change in % CGM wear from 12 weeks to 24 weeks
- Change in glucose metrics from 12 weeks to 24 weeks.
- Change in insulin dose from 12 weeks to 24 weeks.
- Patient reported barriers to continued CGM use (5-point Likert from not important at all to very important, unless otherwise noted):
 - Cost/coverage concerns (if important or very important, then answer the following)

- Insurance did not cover CGM (yes/no)
- Insurance partially covered CGM but co-pay was too high (yes/no)
- Usual care provider would not prescribe CGM (yes/no)
- Too much hassle to order/obtain CGM
- Too many alarms
- Having device attached to the body/lack of privacy
- Do not understand what to do with the information
- Unreliable/does not work
- Discomfort/pain
- Too time-consuming
- Interferes with sleep
- Healthcare utilization (PCP visit, education visit, endocrinology visit, hospital readmission, emergency visit)

Sample Size

We anticipate enrollment of 120 patients over a 1 year period with 20% drop-out. The following data support this sample size.

Aim 1:

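### The week-12 patient-reported outcomes are tied to an in-person visit with no remote route, so Aim 3 rests on attenders and is open to avoidable, probably selective, missing data.

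*Combined protocol and SAP*

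**What the plan says.** Follow-up Encounters sets the rule: "in-person visits are only required for the completion of A1c and patient reported outcomes surveys"; the remaining visits may be done by telephone. It places both items at one contact: "At the 12 week visit, patients will complete patient-reported outcomes surveys and A1c". Table 5 marks week 12 with a different symbol from the telephone visits. Its footnote allows conversion in one direction only: "Telephone visits may be converted to in-person visits as needed". Nothing allows an in-person visit to become a telephone one.

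The Aim 3 primary endpoint is "Change in DTSQ scores from baseline to 12 weeks". Change in DDS and the BenCGM and BurCGM scores are secondary. In Table 5, BenCGM and BurCGM are collected once, at week 12. The Analysis section regresses patient-reported outcomes on percent CGM wear time and states no method for missing data.

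Only the provider survey is described as web-based. Human Subjects, section A.1.a, has completed patient questionnaires scanned into REDCap. The Retention paragraph provides repeated contact attempts, a letter or email, secondary contacts, record review, queries to primary care, and an incentive for the 12-week A1c.

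**The concern.** The plan treats questionnaires as if, like a point-of-care assay, they needed the patient in the clinic. Yet every participant must have a compatible smartphone, email addresses are collected, REDCap is web-based, and calls are already scheduled.

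The other aims have some fallback. CGM data arrive remotely through Clarity, and record review or a primary care query may recover an A1c or a readmission. A missed satisfaction, distress or burden score cannot be recovered that way. The protocol's main answer to loss to follow-up is better telephone contact, but a successful call does not yield a survey that must be done in person.

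The missing scores are probably not a random subset. Patients who return are plausibly more engaged, which would push satisfaction up and burden down and thin out the low-wear end of the wear-time analyses. This direction is inference; the documents give no figure for it.

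**Working it through.** **1. The plan's own figures.** Aim 3 states no sample size or power. The drop-out assumption (Sample Size) gives 120 × 0.80 = 96 patients. The other planning number is 80, used under Aims 1 and 2. As a check on method, the Aim 1 A1c statement (n = 80, difference 0.4, SD 0.9, alpha 0.05, taken as two-sided) gives Φ(0.4/(0.9/√80) − 1.96) = 0.978, or 0.975 by noncentral t, against the stated 98%. It reproduces.

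**2. The only week-12 availability figure from a similar population at this centre.** Preliminary Data, Hospital Discharge Study: "A1c was available in 27 subjects in each arm at 12 weeks", with 82 + 76 = 158 enrolled. So (27 + 27)/158 = 54/158 = 34.2% (95% Wilson interval 27.2% to 41.9%). Applied to 120 patients: 120 × 0.342 = 41 (33 to 50).

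**3. The gap.** 96 − 41 = 55. The documents do not say how many of these patients would answer by telephone or online, so between these two rates the number recoverable is 0 to 55.

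**4. What smaller numbers would do to Aim 3.** All tests are two-sided at 0.05.

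| Quantity | n = 96 | n = 80 | n = 41 |
|---|---|---|---|
| Power, DTSQc shift of 0.29, SD 0.77 | 95.5% | 91.4% | 65.3% |
| Same, SD 0.83 | 92.3% | 87.0% | 58.8% |
| Smallest wear-time correlation detectable with 80% power | 0.28 | 0.31 | 0.43 |
| 95% CI half-width for a mean change, in SDs of change | 0.20 | 0.22 | 0.32 |

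- Rows 1 and 2 use a one-sample noncentral t. The shift is 2.47 − 2.18 = 0.29, and the SDs are those of the two arms of the cited flash-monitoring study (Sample Size, Aim 3). Using a between-group difference as a one-sample shift is an assumption.
- Row 3 is tanh((1.96 + 0.84)/√(n − 3)).
- Row 4 is t(0.975, n − 1)/√n. The interval at n = 41 is 0.316/0.203 = 1.56 times as wide as at n = 96.

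**5. DDS.** The anticipated change is 2.67 − 1.85 = 0.82, with SD 0.65 at each time. The SD of change is 0.65 × √(2(1 − r)). The documents do not give r, so a range is shown.

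| r | SD of change | Half-width, n = 96 | Half-width, n = 41 |
|---|---|---|---|
| 0 | 0.92 | 0.19 | 0.29 |
| 0.5 | 0.65 | 0.13 | 0.21 |
| 0.7 | 0.50 | 0.10 | 0.16 |

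Power for a change of 0.82 exceeds 99.9% at n = 41 throughout this range. For DDS the issue is therefore who answers, not how many.

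**The case against.** **The 34% does not measure this flaw.** A reader might infer that the in-person rule will leave Aim 3 with about 41 patients. The documents do not support that. The figure is A1c availability, not attendance or survey completion, and of that trial the protocol says: "The study was stopped early due to feasibility concerns during the pandemic". It does not say how many of the 158 had reached week 12 by then. Nor can the whole gap be blamed on the in-person rule, since patients who cannot be reached by telephone are not recovered by a telephone option. This objection stands; the figure is only a warning.

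**Burden is recorded elsewhere.** A reader might infer that a patient who stops CGM because of burden and does not return never reports it. That is too strong. Aim 2 records the reason for wear below 70%, adverse events are collected at every follow-up contact, and week 24 asks about barriers such as alarms, discomfort and hassle. What is lost is the BurCGM score, which is the measure Aim 3 analyses.

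**Attendance is sought anyway.** The A1c already calls for the visit, with an incentive, so the surveys add no extra trip. This is true, but it does not help those who still do not come.

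**Remote completion mixes modes.** Trained interviewers collect the initial data. Remote scores would come exactly from patients who missed the visit, so mode and non-attendance are confounded and recording the mode cannot separate them. This stands as a limitation, but it costs less than having no score. No patient-facing REDCap survey is described either, so one would have to be set up.

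**Conclusion.** The point holds as a cheap improvement. The protocol requires attendance for the week-12 patient-reported outcomes, gives no reason for doing so, and offers no fallback for patients who miss the visit but remain reachable. Aim 3 is thereby exposed to avoidable and probably selective missing data.

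Its size cannot be computed from the documents. The bracket of 41 to 96 patients rests on two rates: the earlier trial's A1c availability, which is likely pessimistic for this study, and the planned 20% drop-out. Within that bracket the harm is selection, together with lost precision for the DTSQ and for the wear-time associations. The expected DDS change would remain detectable at the lower end.

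**What to change.** Amend Follow-up Encounters to read, in substance: 'An in-person visit is required only for A1c. The week-12 DTSQs, DTSQc, DDS, BenCGM and BurCGM are completed at that visit or, if it is not attended, by telephone or REDCap e-survey within the week-12 window, including by patients who have stopped CGM.' Align Table 5 and its footnote.

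Record the mode of completion. In the Analysis section, add a sensitivity analysis with and without remote completions, and state that mode and non-attendance are confounded. If BenCGM and BurCGM are also asked when CGM is stopped early, report those scores separately from the week-12 scores, because they refer to a different point of use.

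The cost is a minor amendment, a patient-facing survey link or call form, and some mixing of modes. Sample size and treatment are unchanged.

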Study Extension: Patients will transition to standard of care observational extension phase of the study in order to ascertain whether patients continue use of CGM through their usual care provider. General instructions will be provided to the patient and provider based upon the patient's payer (including use of durable medical equipment company or pharmacy). We will assess device use, glucose metrics, medication adjustments, healthcare utilization, and A1c.

Provider survey: At 12 weeks, Clinicians will be contacted via email to participate in a web-based survey. Participants provided electronic informed consent prior to taking the survey. The survey is anticipated to take approximately 15 minutes. An incentive in the form of a \$20.00 Amazon gift card will be electronically distributed to providers who complete the survey. Survey elements will include:

- Practice characteristics: provider type, years in practice, practice setting, specialty, characteristics (percentage of patients with diabetes, familiarity of CGM use [5-point scale], frequency of interpreting CGM reports).
- Utility of CGM reports to make adjustments to therapy. There is no validated survey specifically assessing utility of CGM reports for clinicians. The Sustainability Use Survey (SUS), a 10-item questionnaire, is widely used for measuring perceived usability of a system.⁵⁵ The SUS-2 is the best combination of SUS items that predict an SUS score with high accuracy; therefore, the 2 items were included in the provider survey in lieu of using the full SUS to enable benchmarking of usability and minimize provider burden. The 2 items used in the CAS are: 1) *I thought the CGM report was easy to use*, and 2), *I found the CGM report was cumbersome to use*. These questions map to SUS 03 and SUS 08, respectively, and when analyzed together are known as the SUS-2. The questions are analyzed based upon a 5-point Likert scale. Benchmarking SUS scores: SUS-2 scores and individual item scores have been compared against a large dataset of ~500 published studies of SUS data. The average raw SUS score (at the 50th percentile) is 68.
- Additional questions will include (5-point likert scale)
 - *I found the Ambulatory Glucose Profile to be helpful for assessing glucose control*
 - *I found the Ambulatory Glucose Profile to be helpful for making adjustments to therapy*
 - *I found the report recommendations to be helpful for making adjustments to therapy*

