The database used for this study is REDCap, which is a secure web-based application for building and managing data. It is designed specifically for clinical research and administered by the OSU Center for Clinical and Translational Research. Permission for data access or entry will be granted or revoked at a level that is appropriate for each individual involved in the study. Following verification, data will be locked. Data and data labels can be downloaded selectively (for interim progress reports) or in entirety (end of study) directly from REDCap in SAS or Excel format.

Baseline Data:

- Demographics: gender, race/ethnicity, age, marital status, education, employment, insurance, marital status, contact information
- History: diabetes duration, tobacco use, microvascular/macrovascular complications, heart failure, conditions requiring anticoagulation (thromboembolism, atrial fibrillation), hypertension, hyperlipidemia, liver disease, hypoglycemia awareness, reason for hospital admission
- Medications: pre-admission, discharge, and follow-up insulin use and total daily dose, insulin type, other glucose-lowering medications, steroid use, anticoagulants, antiplatelets
- Exam: weight, height, BMI
- Surveys: MPSSS, eHEALS, SNS-3
- Labwork: eGFR, A1c, glucose level on admission and discharge
- Patient reported outcomes: DTSQs, DDS
- Additional patient questions about CGM use
- CGM target (Table 4)

Visit 1, 2, 3:

- Glucose data: detailed below
- Communication: to usual care provider (summary only, summary with advice)
- Diabetes medications, bolus insulin use, basal insulin dose, missed doses
- Adverse events (sensor irritation, infection, bleeding)
- Additional patient questions about CGM use
- Healthcare Utilization: PCP visit, education visit, endocrinology visit, hospital readmission, emergency visit
- CGM target (Table 4)

Visit 4:

- Glucose data: detailed below
- Communication: to usual care provider (summary only, summary with advice)
- Diabetes medications: non-insulin medication use by class, bolus insulin use, basal insulin dose, missed doses
- Adverse events (sensor irritation, infection, bleeding)
- Healthcare Utilization: PCP visit, education visit, endocrinology visit, hospital readmission, emergency visit
- Patient reported outcomes: DTSQs, DTSQc, DDS, BenCGM, BurCGM
- Additional patient questions about CGM use
- A1c
- CGM target (Table 4)

Visit 5, 6

- Glucose data: detailed below

Visit 7

- Glucose data: detailed below

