Based upon preliminary data, we found that approximately 30% were of African American race. We are enrolling a wide age range, 25-75, in order to achieve optimal external validity. Participants are anticipated to be sick and have other comorbidities (in our pilot data, 70% were admitted for a problem that was not directly related to diabetes). However, all participants will be free-living in the community and have a phone. Due to bias introduced by additional support staff at institutions such as nursing homes and rehabilitation centers, these participants will be excluded. Participants who are unable to provide consent in English will be excluded as this number is very small and educational materials from the manufacturer are not available. Other vulnerable populations, such as prisoners will be excluded. Pregnant individuals will be excluded since the A1c is not as reliable, glucose targets differ, and because such individuals have different motivations and follow-up already in place.

Permission will be obtained from the attending physician of the admitting inpatient service prior to approaching participants for enrollment. The frequency of follow-up is felt to be adequate to establish reasonable endpoints for reinforcement of behavior and capture a realistic window for readmission.

The patient's usual care provider (primary care or endocrinologist) will be identified from the electronic medical record and via patient self-report. Providers will be invited to anonymously respond to the survey via an electronic communication (Inbox message, email, or letter with a URL link—in case of external provider). Up to 2 providers per patient, primary care and endocrinologist, up to 200 providers total will be contacted.

A.1.b. *Sources of Materials*

Baseline Data:

- Contact information, including email address and best times to reach the patient, contact information for two emergency contacts, and contact information of the patient's usual diabetes care provider
- Demographics: gender, race/ethnicity, age, marital status, employment, contact information, discharge location

- History: diabetes duration, tobacco use, microvascular/macrovascular complications, heart failure, conditions requiring anticoagulation (thromboembolism, atrial fibrillation), hypertension, hyperlipidemia, liver disease, hypoglycemia awareness, reason for hospital admission

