Recruitment and Informed Consent

Potential participants will be identified during their hospitalization through screening inpatient endocrine consults as well as review of non-ICU medicine and surgery wards. A HIPAA waiver will be obtained for this purpose. The patient will be approached in private. Personnel (coordinator) will describe the purpose of the study in the same words that are used on the consent form, which states lack of participation will not otherwise influence patient care. Participants are expected to read the consent form (or have it read to them) in full and be able to explain the study purpose, risks, and procedures to the investigator before consent will be considered complete and informed. Participants that seem unsure or want to consider it further will be re-approached with their permission, after several hours or the following day or otherwise per the participant's request. The samples and study-related information will not be used and the participant will be withdrawn if the participant subsequently declines enrollment.

Usual Care Providers: providers will be contacted by electronic inbox, email (internal providers), or mail (if external to OSU) and will be invited to provide feedback. There is no obligation to proceed and individual responses will not be tracked or traceable.

Protections against risk

Participants will receive instruction for use of the glucose monitoring device, including interpretation of data, limitations of use, and recognizing and addressing sensor irritation issues.

Participants will be assigned a study number that will be the primary means of identifying patient data. A key will be kept on the secure endocrine network drive but this will only be for internal investigator use. Any personal information acquired will be entered into the secure online database (Redcap), which is password protected, and allows limited access to varying degrees. Only immediate study staff (PI, nurse, research assistants) will have access to Redcap. Other personal information (such as signed consent forms) will be

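### The provider item on whether recommendations helped is put to all surveyed providers, including any who were sent none, and the plan describes no way to separate them

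*Combined protocol and SAP*

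**What the plan says.** **Letters.** The section Communication with Usual Care Providers sets two kinds of letter, decided at each of four contacts. When the patient is not at target, the provider gets a CGM summary and an account of the counselling given, "as well as any additional advice to the usual diabetes care provider using a standardized template". When the patient is at target, "a summary letter with Ambulatory Glucose Profile will be sent to usual care providers at weeks 1-2, 4, 8, and 12", and no advice is mentioned. The data collection lists for Visits 1 to 4 log which kind was sent: "Communication: to usual care provider (summary only, summary with advice").

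**Survey.** The Provider survey section says: "At 12 weeks, Clinicians will be contacted via email to participate in a web-based survey". The Human Subjects section sets the numbers: "Up to 2 providers per patient, primary care and endocrinologist, up to 200 providers total will be contacted". Neither restricts the survey by type of letter. One of the 5-point items reads "I found the report recommendations to be helpful for making adjustments to therapy". Under Endpoints, Aim 2, Secondary, it appears within the provider usability bullet as "report recommendations helpful for making adjustments to therapy", with no denominator. The Analysis section adds none.

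**Anonymity.** Recruitment and Informed Consent says of providers that "individual responses will not be tracked or traceable". Protections against risk adds that the link is anonymous and that no identifiers are collected.

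**The concern.** The schedule expects some letters to carry no recommendations, and the data collection records that distinction. The survey does not carry it over. A provider who received only summaries is still asked how helpful the recommendations were, and any answer given (neutral, negative, or positive about the report as a whole) enters the same tally as ratings of actual advice.

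The letter-type log sits on the patient side and cannot be joined to untraceable responses, so the two groups cannot be separated after collection. Aim 2 says the provider survey will assess the usability of both reports and decision support. The other opinion items concern the CGM report and the Ambulatory Glucose Profile, so this is the only one that asks providers to judge the advice. At stake is whether that single rating has an interpretable denominator.

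**Working it through.** The plan states no figure for this item, so there is none to reproduce. The check has two parts.

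**1. Can a surveyed provider have received no recommendations, and would the data show it?**

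- Receipt: a provider has none to rate if the patient met targets at all four contacts (weeks 1-2, 4, 8 and 12), or if the letters sent after missed targets carried no additional advice.
- Survey content: the lists under Provider survey, Data Collection and Management, and Sources of Materials cover seven practice items, two SUS-2 items, three helpfulness items and Clarity access. That is 7 + 2 + 3 + 1 = 13, against a stated 12. None asks whether advice was received.
- Linkage: none, because responses are anonymous.

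**2. How much could it matter?**

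Let s be the share of respondents who received no recommendations, pA the agreement among recipients and pN the agreement among the rest.

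- Pooled agreement = pA(1 − s) + pN·s, so the shift is s(pA − pN).

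The documents give none of these three. For s, assume one patient per provider and advice in every letter sent after a missed target. Then:

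- Chance of meeting target rising 30%, 40%, 50%, 60% over the four contacts (assumed), independent: s = 0.3 × 0.4 × 0.5 × 0.6 = 0.036.
- 60% at each contact, independent: s = 0.6⁴ = 0.1296. The 60% is the share that the Sample Size section, Aim 1, anticipates will meet individualized time in range. Applying it to every contact is an assumption.
- The same 60% of patients always at target: s = 0.60.

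At 200 respondents, the ceiling on providers contacted, these shares are about 7, 26 and 120 providers. With pA = 80% (assumed):

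| s | pN = 0% | pN = 30% | pN = 50% |
|---|---|---|---|
| 3.6% | 77.1% | 78.2% | 78.9% |
| 13.0% | 69.6% | 73.5% | 76.1% |
| 60% | 32.0% | 50.0% | 62.0% |

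Example: 0.8 × 0.8704 + 0.3 × 0.1296 = 0.696 + 0.039 = 0.735. With the denominator limited to recipients, every cell returns to 80%.

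**The case against.** The strongest reply is that the affected group may be very small. Letter type is set at each contact, so one letter with advice in 12 weeks is enough to make a provider a recipient. Patients enter with A1c above 8.0%, and Table 4 lists goals for time above and below range as well as time in range, so being at target four times running may be uncommon. A provider with several enrolled patients lacks advice only if none of those patients prompted any. All of this stands. A reader might infer a large dilution, with a share of perhaps 20-50% pulling 80% down to 55-70%. Shares of that size need the same patients to be at target from the first contact onward, or advice often omitted after missed targets, and the documents support neither.

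Three other stronger readings also fail.

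- That the questionnaire offers no not-received choice: the instrument is not in the documents. All that can be said is that the protocol describes none.
- That duplicate responses will occur and go undetected: nothing says a provider is invited once per patient. Invitations are addressed to identified providers, the total is capped at 200 (against 120 × 2 = 240 possible), and gift cards are sent to completers, so repeats might be visible at invitation or payment.
- That the evaluation of decision support depends on this item: it is one element of one secondary bullet. Aim 2's primary endpoint is CGM wear time, and advice sent and change in basal insulin dose are assessed separately.

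The reply does not remove the structural point. Whether the share is 4% or 60%, the survey responses would not show it, and the patient-level count of advice sent cannot be attached to them.

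**Conclusion.** The point holds as a modest defect in one secondary item. As described, the plan may pool ratings of advice with answers from providers who received none, and the pooling could not be undone after collection.

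The size is unknown. The share without recommendations could be near zero. It is about 4% to 13% in the two independent-contact scenarios and reaches 60% only if the same patients are always at target. With agreement of 80% and 30% assumed, the pooled figure is about 78%, 73.5% or 50%. If both groups answered alike there would be no shift. No primary endpoint, power calculation or success criterion is touched. The case for acting is that the remedy is cheap and is available only before responses are collected.

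**What to change.** Add one yes/no item ahead of the rating, *I received treatment recommendations from the study*, or add a 'not received' choice to the rating itself. Show or analyse the recommendations item only for those answering yes. State in the Aim 2 endpoint that its denominator is providers reporting receipt, and report that number alongside the result.

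The cost is one extra survey item, an IRB wording change and a slightly smaller denominator. Anonymity is kept. The stated item count should be corrected at the same time.

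A sensible minor addition is to invite each provider once, from a de-duplicated list.
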